2.1. Participants

Inclusion criteria included the following: male sex; age 37–65; presence in the Persian Gulf region between August 1990 and August 1991; ability to come to the study site for 11 monthly visits; ability to receive a venous blood draw; and successful completion of \geq 80% of daily symptom reports over the baseline period. All participants had to fulfill Kansas Gulf War Illness case criteria [33], with an exception for well-controlled diabetes mellitus type 2 (A1C \leq 9%) and in one case for an individual with a history of cancer outside of the last 5 years (Hodgkin's lymphoma in remission for 20 years). In such cases of unclear decisions for inclusion, the author of the Kansas GWI case criteria was consulted for guidance.

Individuals were excluded from study participation for the following: current daily use of opioid or anti-inflammatory medications; use of nitroglycerine or lithium; history of anaphylaxis to any botanical used in the study; hypotension (<90/60 mmHg) or history of cardiovascular disease; diagnosis of rheumatologic or autoimmune disease; blood or clotting disorder; current litigation of worker's compensation claim; and inability to read and understand English. Baseline exclusionary criteria also included acute infection (body temperature above $100.4~^\circ\text{F}$), positive rheumatoid factor (RF), positive antinuclear antibody (ANA), erythrocyte sedimentation rate (ESR) > 40~mm/hr, and CRP > 10.0~mg/L. Individuals with current severe depressive symptoms as suggested by a depression subscale score $\geq 16~\text{on}$ the Hospital Anxiety and Depression Scale (HADS; [34]) were excluded. Current Posttraumatic Stress Disorder (PTSD) was also exclusionary. Individuals with scores $\geq 50~\text{on}$ the PTSD Checklist–Military Version (PCL-M; [35]) were assessed for the presence of current PTSD with the Clinician Administered PTSD Scale (CAPS-5; [36]).

2.2. Treatments

Resveratrol was sourced from Pure Encapsulations (Sudbury, MA, USA) and was standardized to contain 20% trans resveratrol. Luteolin was obtained from A.P.I. Solutions (Daphne, AL, USA), and fisetin was sourced from VitaCost (Boca Raton, FL, USA). All

botanicals were sent to Double Oak Mountain Pharmacy in Birmingham, AL, USA, where they were re-encapsulated in size 0 or 00 opaque blue gelatin capsules. Microcrystalline cellulose was used as filler for the placebo treatment, with the same blue covering capsules as the botanical compounds, so that all treatments appeared identical. All capsules were placed in standardized QUBE Weekly (28 cavity) Cold Seal Compliance Blister Packs (Pharmacy Automation Supplies, Romeoville, IL, USA).

Treatments were administered twice a day. The lower dose for resveratrol was 200 mg/day (200 mg in morning and 0 mg in evening), and the higher dose for resveratrol was 600 mg/day (400 mg in morning; 200 mg in evening). For luteolin, the lower dose was 200 mg/day, and the higher dose was 400 mg/day. Fisetin was administered at 200 mg/day for the lower dose and 800 mg/day for the higher dose. For both luteolin and fisetin, total dosage was evenly split between morning and night doses.

2.3. Study Protocol

The study protocol is depicted in Figure 1. Interested individuals completed an online prescreening questionnaire prior to a phone interview with research personnel in order to assess for initial eligibility. For individuals who met initial inclusion criteria, an in-person screening visit was held at the UAB Center for Clinical and Translational Science Clinical Research Unit (CRU). All participants provided written informed consent at the in-person screening. Baseline study questionnaires were administered on a tablet device, and vital signs and venous blood samples were collected by CRU staff to assess for exclusionary laboratory values. Participants were also provided with computer tablet devices to take home with them in order to complete once daily symptom reports during the entire study period. A one-month baseline symptom reporting period began immediately following the in-person screening visit. Participants were required to complete at least 80% of daily symptom reports during this period to remain eligible for the study.

[figure not shown]

Figure 1. Study protocol. Each participant completed testing of up to three botanicals. For each botanical, there was a placebo condition, followed by lower-dose botanical and higher-dose botanical conditions. The period of time between visits was 30 ± 3 days. Some participants reenrolled in the study after completion, receiving up to a maximum of six botanicals.

Pseudo-randomization was then performed so that participants were assigned to receive up to three out of the nine botanical compounds, as shown in Figure 1. Pseudo-randomization was done in such a way to prevent drug interactions that contraindicated the use of the botanical in a given participant. There were no contraindications for the use of luteolin. Because blood glucose may be lowered by resveratrol [37] and fisetin [38], individuals taking medications for diabetes, or with evidence of prediabetes or diabetes, were excluded from taking these agents.

Additionally, individuals with clotting disorders, hypotension, or those taking anticoagulants or

Additionally, individuals with clotting disorders, hypotension, or those taking anticoagulants or antihypertensive medications were excluded from taking resveratrol, due to its effects on blood pressure [39,40]. Prophylactic use of 81 mg aspirin daily was permitted.

All study visits were held at the CRU and were conducted once a month for 10 months after completion of the baseline period. Participants received kits at each visit containing a one-month

supply of either placebo or botanical capsules. Kidney and liver function were monitored with blood draws conducted at visits 4, 7, and 10. The following laboratory values were tested at those visits: sodium, potassium, chloride, bicarbonate, anion gap, glucose, blood urea nitrogen, creatinine, calcium, phosphorus, albumin, total protein, total bilirubin, direct bilirubin, indirect bilirubin, alkaline phosphatase, aspartate aminotransferase (AST), and alanine aminotransferase (ALT).

The same protocol (one month of placebo, one month of lower-dose botanical, and one month of higher-dose botanical) was completed for each botanical. For safety reasons, lower-dose conditions always preceded higher-dose conditions, allowing adverse effects to be detected before a higher dose of the agent was used. Only the study pharmacist was unblinded to the assigned botanicals. All other study staff were aware of the design condition order, but were blinded to the specific botanical taken by each participant. Participants were blinded to both the administration order (placebo, lower-dose, and higher-dose) and the botanical compounds.

Treatment adherence was monitored at each study visit. Each month, participants were instructed to return their blister packs. Study staff checked for any missed doses and discussed with participants the importance of adhering to the administration regimen. Participants were provided with the option of re-enrolling in the study after completing the protocol, such that they could be assigned up to a total of six out of the nine compounds.

2.4. Screening Measures

Participants were screened for GWI using the Kansas Gulf War Illness (GWI) case definition [33], in which symptoms are rated in severity from 0 (none) to 3 (severe). Inclusion criteria were met if an individual obtained a score of 2 or greater (indicating at least one moderate symptom or two mild symptoms) across three or more of six symptom domains (pain, fatigue, neurological/cognitive/mood, gastrointestinal, respiratory, and skin). Symptoms were required to have begun during or after Gulf War service. Chronic medical conditions not associated with Gulf War military service (including heart disease, stroke, lupus, multiple sclerosis, cancer [other than skin cancer], melanoma, and liver disease) were exclusionary for case definition. Due to the possibility of impacting a participant's ability to report symptoms, the following other conditions were exclusionary per case criteria: bipolar or manic depression, schizophrenia, and recent hospitalization for alcohol or drug dependence, depression, or PTSD.

Participants were screened for symptoms of severe depression with the HADS [34]. This questionnaire was part of the online pre-screening process and was completed using the Qualtrics Research Suite Online Application. The 14 items of the HADS contain subscales for Anxiety (HADS-A) and Depression (HADS-D), each with 7 items. Items are rated from 0 to 3, and reverse scoring is used for 5 of 14 total items. Higher ratings suggest greater symptomatology. All ratings are summed for a total score ranging from 0 to 42.

Participants were also screened for severe symptoms of PTSD using the PCL-M [35]. Like the HADS, the PCL-M was completed during the online pre-screening process using the Qualtrics Research Suite Application. The 17-item PCL-M reflects PTSD diagnostic criteria of the fourth edition of the Diagnostic and Statistical Manual of Mental Disorders (DSM-IV; [41]). Each item inquires about trauma and stress symptoms associated with military experiences (e.g., Repeated, disturbing memories, thoughts, or images of a stressful military experience?) and is rated on a Likert scale from 1 (not at all) to 5 (extremely). Scores of 50 or greater suggest an increased likelihood of meeting DSM-IV diagnostic criteria for PTSD [42].

If a PCL-M score of 50 or above was obtained, potential participants were evaluated further for current PTSD symptoms using the last month version of the CAPS-5 [36]. Personnel of the UAB Office of Psychiatric Clinical Research administered the CAPS-5 at the CRU during the inperson screening visit. The CAPS-5 is a structured interview consisting of 30 items assessing PTSD symptom severity and diagnostic status (symptom duration and onset, distress levels, impact on social and occupational functioning, response validity, and dissociative subtype symptoms). Items are rated with a severity score based on frequency and intensity of symptoms. A symptom that meets the threshold for diagnosis of current PTSD is suggested by a severity rating of 2 ("Moderate/threshold").

2.5. Main Outcome Measures

Participants reported their symptoms once daily in the evening via the Qualtrics Research Suite Offline Application (Qualtrics, Provo, UT, USA). The reports consisted of visual analog scale (VAS) ratings of symptoms scored from 0 to 100. Given that GWI consists of multiple idiosyncratic symptoms, a single-item severity score was chosen as the primary outcome to provide a common measure for GWI symptom severity. The main outcome was assessed with the following question, "Overall, how severe have your symptoms been today?" with "Not severe at all" fixed on the far left and "Extremely severe" fixed on the far right. Research personnel instructed participants to rate their daily overall GWI symptom severity based on their particular GWI symptoms, encompassing all possible six GWI domains.

2.6. Secondary Outcome Measures

In addition to the GWI symptom severity item, participants responded to several other daily single-item measures. These items assessed specific symptoms including pain, fatigue, cognitive dysfunction, depressed mood, skin problems, respiratory complaints, and gastrointestinal issues. A sufficient number of participants endorsed the pain and fatigue items so that statistical analyses could be applied. Participants responded to pain and fatigue questions using two separate 0–100 VAS ratings. To assess pain, participants were asked, "Overall, how severe is your pain?", with "No pain at all" fixed on the left and "Severe pain" on the right. The item regarding fatigue asked, "How fatigued have you felt today?", with "Not fatigued at all" fixed on the left and "Severely fatigued" on the right.

2.7. Statistical Analyses

SPSS Statistics for Windows, version 24 (IBM Corp., Armonk, NY, USA) was used to conduct analyses. Linear mixed models (LMM) were utilized to test differences in self-reported symptom severity between the four conditions. A separate model was tested for each of the three botanicals. Subject ID was entered as the subject identifier, with all individual longitudinal data nested within-person. The participant's day in the study was entered as the index variable for repeated measures. Compound symmetry was selected as the repeated measures covariance type. The AR (1) autoregressive covariance type was also considered, but it did not improve the Akaike information criterion (AIC) or Bayesian information criterion (BIC) for model performance. The dependent variable was daily GWI symptom severity (0–100). Treatment condition (baseline,

placebo, lower-dose, and higher-dose) was entered as a fixed factor. The last 14 days of each condition were selected for analyses to permit time for clinical effects of the treatments to occur. A restricted maximum likelihood (REML) estimation approach was used. Statistical significance was set at p < 0.05 for all tests. The secondary analyses were conducted using the same approach.

We performed a-priori power analyses using G*Power 3 [43] to estimate sample size. Each of the nine botanical trials was powered to detect a medium effect (Cohen's d = 0.5) at 0.99 power with p = 0.05 threshold for significance. Given 56 repeated outcome measurements per participant (with a repeated measures correlation of 0.5), each trial required 10 individuals to obtain 0.99 power. Our studies were not powered (0.42 predicted power) to detect small effects (Cohen's d = 0.25).

A Placebo-Controlled, Pseudo-Randomized, Crossover Trial of Botanical Agents for Gulf War Illness: Reishi Mushroom (Ganoderma lucidum), Stinging Nettle (Urtica dioica), and Epimedium (Epimedium sagittatum)

2. Materials and Methods

This report is part of a larger clinical trial in which nine botanical agents were tested for effects in GWI. A pseudo-randomized, placebo-controlled, crossover design was used. Curcumin, boswellia, maritime pine, epimedium, fisetin, luteolin, reishi, resveratrol, and stinging nettle were tested in the larger study. In this paper, the results of reishi, stinging nettle, and epimedium are discussed. All procedures were approved by the Institutional Review Board of the University of Alabama at Birmingham (UAB: F150318011) in June 2015, and the trial was registered on ClinicalTrials.gov (NCT02909686) accessed on 21 September 2016.

2.1. Participants

Individuals screened for the study were men between the ages of 44 and 65 who met the Kansas GWI case criteria [34] and were deployed to the Persian Gulf region between 1990 and August 1991. As participants must have been at least 18 years old during the Persian Gulf War, the youngest possible age at the study start in 2016 was 44 years. All inclusion and exclusion criteria in the Kansas GWI criteria were utilized, with the exception that individuals with diabetes type 2 could participate. Individuals with diabetes could participate only if the disease was medically controlled, with hemoglobin A1C below 9%.

Individuals were excluded from participation if they were taking opioid analgesics, anti-inflammatory medications, nitroglycerine, or lithium, or if they reported allergies to any study compounds. Participants could not have blood/clotting disorders, hypotension (below 90/60 mmHg), cardiovascular disease, rheumatologic disorders, autoimmune conditions, or acute infection with a body temperature over 100.4°F. Individuals could not participate if their laboratory blood values showed an erythrocyte sedimentation rate greater than 40.0 mm/Hr, a Creactive protein value greater than 10.0 mg/L, or positive rheumatoid factor or antinuclear antibody.

Individuals were also excluded if they scored 16 or greater on the Hospital Anxiety and Depression Scale (HADS; [35]) depressive subscale by summing the depression items rated on a 0 to 3 scale. Significant posttraumatic stress disorder (PTSD) was identified if individuals scored equal or greater than 50 on the 17-item PTSD Checklist—Military Version (PCL-M; [36]). Individuals with possible ongoing PTSD were subsequently assessed by a member of UAB's Office of Psychiatric Clinical Research, using the Clinician Administered PTSD Scale (CAPS-5; [37]). The 30-item structured interview was used to make a final determination of current PTSD, using established criteria [38]. Individuals meeting criteria for current PTSD were excluded from the study.

2.2. Botanicals

Reishi was sourced from JHS Natural Products, Mushroom Science (Eugene, OR, USA) as a hot water and alcohol extract with 12% polysaccharides and 4% triterpene. Stinging nettle was

procured from Nature's Way (Green Bay, WI, USA) as pure nettle leaf. Epimedium was from Barlowe's Herbal Elixirs (Palm Beach, FL, USA) as a 20% icariin extract. Procured agents were sent to a compounding pharmacy (Double Oak Mountain Pharmacy, Birmingham, AL, USA) for re-encapsulation. Materials were put in size 0 or 00 blue gelatin capsules and organized in weekly Cold Seal Compliance blister packs (Pharmacy Automation Supplies, Romeoville, IL, USA). Participants and research personnel were blinded to the botanical agent assignments.

Reishi was administered at 1600 mg (lower dosage) and 3200 mg (higher dosage) per day. Epimedium was given at 500 mg and 1000 mg per day (100 mg and 200 mg of icariin, respectively). Stinging nettle was given at 435 mg and 1305 mg per day. All botanicals were administered twice per day (morning and evening), with the total daily dosage being split evenly between the morning and evening doses. Placebo was administered in identical gelatin capsules with microcrystalline cellulose filler.

Individuals on any antihypertensive medications were not allowed to take reishi or epimedium, even if their blood pressure was well-controlled. Individuals were not assigned to take stinging nettle if they had any signs of diabetes, pre-diabetes, or were taking medications for diabetes. Individuals could participate in the study despite being excluded from taking one or more of the botanicals, as the entire list of nine botanicals had several contraindications. As many individuals with GWI also suffer from conditions such as high blood pressure and diabetes, excluding these individuals would have created a sample that is not representative of the general patient population.

2.3. Study Protocol

Individuals were screened via an online questionnaire and phone interview, followed by an in-person screening conducted at UAB's Clinical Research Unit (CRU). Informed consent was obtained at the in-person visit, and blood samples were collected for further screening. As the screening involved blood tests, individuals provided informed consent before being determined eligible for participation. Therefore, several individuals who provided consent were not eligible to participate in the study. Consented individuals received a tablet device for completing daily symptom reports each evening for the duration of their study participation.

Before beginning capsules, all participants completed a baseline period of 30 days. This period served as the baseline for all botanicals taken by the participant. Participants then were pseudo-randomized to receive up to three of the nine study compounds, as seen in **Figure 1**. A pseudo-randomized procedure was used to avoid contraindications with the botanicals. Randomization was conducted by a pharmacist. The pharmacist in charge of blinding and randomization was not otherwise involved in the study. The research personnel were blinded to the botanicals assigned to each participant. For each botanical, participants completed 30 days of placebo capsules, 30 days of lower-dose botanical, and 30 days of higher-dose botanical. Participants were blinded to all aspects of the study (the protocol and botanicals assigned). Research personnel were blinded to the botanicals assigned, though they were aware that placebo occurred first, followed by lower-dose and higher-dose treatment.

[figure not shown]

Figure 1. Study event flow. Participants took three of the tested compounds in the following order: placebo, lower-dose botanical, and higher-dose botanical.

Throughout their involvement with the study, participants returned to the CRU every month. At these visits, participants would obtain a new supply of study capsules. Blood samples were also obtained at visits 4, 7, and 10 to conduct safety tests. Standard clinical renal and hepatic panels were performed. Participants first took the lower dosage and then the higher dosage of the botanical so that any renal or hepatic issues could be detected before the participant took the larger dosage. Participants received compensation during each visit. The participants received a total of \$1500 for attending all 11 of the study visits and completing the protocol. Participants who successfully completed all three botanical assignments were allowed to enroll in the study a second time, where they would be assigned new botanicals.

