After the baseline period, participants returned once monthly (every 30 +/- 3 days) for up to 10 additional visits to the CCTS CRU for dispensation of their placebo or botanical capsule kits. At visits 4, 7, and 10, participants received additional blood draws to monitor liver and kidney function (sodium, potassium, chloride, bicarbonate, anion gap, glucose, blood urea nitrogen (BUN), creatinine, calcium, phosphorus, albumin, total protein, total bilirubin, direct bilirubin, indirect bilirubin, alkaline phosphatase, aspartate aminotransferase (AST), and alanine aminotransferase (ALT)). Participants were compensated for each laboratory visit.

For each botanical, participants followed the same protocol: one month (30 +/- 3 days) of placebo, one month (30 +/- 3 days) of lower-dose botanical, and one month (30 +/- 3 days) of higher-dose botanical. Study participants were blinded to both the assigned botanicals and

administration protocol (placebo, lower-dose, higher-dose). This administration order was chosen for safety reasons, i.e., adverse effects could be detected in a lower-dose condition before a higher-dose, with possibly greater adverse effects, would be administered. Research personnel were blinded to the assigned botanicals but not to the administration protocol. The study pharmacist was unblinded to both administration protocol and assigned botanicals but had no contact with study participants. Adherence to botanicals was checked at each study visit when participants returned their used blister packs. If participants had missed doses, study staff reminded them of the importance of a regular dosing schedule.

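### Can panels at visits 4, 7 and 10 both monitor liver and kidney function and catch problems before the higher dose?

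*Combined protocol and SAP*

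**What the plan says.** The document joins three methods reports, each with its own section 2.3 (Study Protocol). They agree on when blood was drawn.

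- Curcumin, boswellia and maritime pine report: "At visits 4, 7, and 10, participants received additional blood draws to monitor liver and kidney function".
- Resveratrol, luteolin and fisetin report: "Kidney and liver function were monitored with blood draws conducted at visits 4, 7, and 10".
- Reishi, nettle and epimedium report: "Blood samples were also obtained at visits 4, 7, and 10 to conduct safety tests".

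Only the third report links the dose order to laboratory findings, saying the lower dose was taken first "so that any renal or hepatic issues could be detected before the participant took the larger dosage". The other two justify the order by adverse effects in general.

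On the calendar, the third report pays participants for "attending all 11 of the study visits and completing the protocol". The first describes, after baseline, "up to 10 additional visits to the CCTS CRU for dispensation of their placebo or botanical capsule kits". The Figure 1 caption in the second report adds: "The period of time between visits was 30 ± 3 days". Each botanical runs through placebo, lower dose and higher dose, one month each, for up to three botanicals per enrolment. No readable sentence gives the screening visit a number, and the study-flow figures are not reproduced in the text available here.

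**The concern.** Three panels over three blocks is one panel per block. Within a block, a single panel can fall before the higher dose or after it, but not both. If it falls before, the higher dose has no panel of its own. If it falls after, nothing checks liver and kidney function between the two doses, and the third report's reason for the dose order fails. Since the visit numbering is not spelled out, a reader cannot tell at once which gap applies.

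What would be at stake is the reach of any laboratory safety statement. The higher dose is two to four times the lower (curcumin 4000/1000 = 4; nettle 1305/435 = 3; reishi 3200/1600 = 2), so a panel taken on the lower dose says little about the higher one. A panel taken two months later, with a different botanical started, could be credited to the wrong agent.

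**Working it through.** This is a calendar count; no power or sample-size formula applies.

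**Inputs.** One baseline month starting at screening; 3 botanicals; 3 months per botanical; visits 30 ± 3 days apart; panels at visits 4, 7 and 10. All come from section 2.3 of the three reports.

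**Reproducing the plan's visit count.** Intervals = 1 + 3 × 3 = 10. Visits = intervals + 1 = 11, of which 10 come after screening. This matches the 11 visits and the 10 additional visits in the reports.

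**Reading A: screening is visit 1.** Visit v falls on day 30 × (v − 1).

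| Visit | Day | Month just ended | Month starting | Panel |
|---|---|---|---|---|
| 1 | 0 | – | baseline | |
| 2 | 30 | baseline | placebo 1 | |
| 3 | 60 | placebo 1 | lower 1 | |
| 4 | 90 | lower 1 | higher 1 | yes |
| 5 | 120 | higher 1 | placebo 2 | |
| 6 | 150 | placebo 2 | lower 2 | |
| 7 | 180 | lower 2 | higher 2 | yes |
| 8 | 210 | higher 2 | placebo 3 | |
| 9 | 240 | placebo 3 | lower 3 | |
| 10 | 270 | lower 3 | higher 3 | yes |
| 11 | 300 | higher 3 | end | |

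- Panel after the lower and before the higher dose: 3 of 3 blocks.
- Panel at the end of the higher-dose month: 0 of 3 blocks.
- Delay from the end of the higher dose to the next panel, botanicals 1 and 2: 2 × 30 = 60 days, ± 2 × 3 = 6, so 54 to 66 days. A placebo month and a lower-dose month of the next botanical lie between.
- Botanical 3: no later panel is listed within the enrolment.

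**Reading B: screening is visit 0.** Visit v falls on day 30 × v, so the panels fall on days 120, 210 and 300.

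- Panel between the lower and higher dose of the same botanical: 0 of 3 blocks.
- Panel at the end of the higher-dose month: 3 of 3 blocks.

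**Which reading fits.** The third report counts 11 study visits, and the first calls the post-baseline visits additional, which puts screening among the 11. Numbering those visits 1 to 11 gives Reading A. The stated purpose of the dose order is also met on Reading A and fails on Reading B.

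**Are both statements met on Reading A?** The third report needs a panel before the larger dose: met in every block. The other two say that function was monitored: met by a panel every three months. None of the three reports claims a panel during or after the higher dose.

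**The case for a change.** The strongest case for a change is that a gap exists on either numbering, so the point does not depend on settling it. Reading B is not far-fetched: the second report describes monthly visits for 10 months after baseline, which someone could number 1 to 10. Even on Reading A, blood is drawn at the visit where the higher-dose kit is handed out, and no text says results were seen before those capsules were taken. Tabulating existing panels by the preceding agent and dose would also cost little.

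Much of this stands as description. One panel per block cannot cover both sides of the higher dose; on the natural numbering the higher dose has no timely panel of its own; and the text is silent on review of results.

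It does not stand as a contradiction. That needs Reading B, which no sentence states and which the missing figure may rule out. It also does not lead to a change in the analysis. The outcomes are daily symptom ratings, and none of the three statistical sections analyses laboratory values. The document holds methods only, so there is no laboratory conclusion to narrow. The one step that would close the gap is adding or moving a draw. That is a matter of clinical management for the sponsor's clinical team, and the study is already described in the past tense.

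**Conclusion.** The concern does not call for a change. On the natural numbering the two statements are compatible: a panel precedes the higher dose in 3 of 3 blocks, and function is checked every three months. Using the single panel per block before escalation is a fair trade-off, and it is the one the third report describes.

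The limit is worth knowing. No higher-dose month ends with a panel (0 of 3), the next draw is 54 to 66 days later for the first two botanicals, and none is listed after the third. An analyst tabulating the panels would sensibly assign each to the agent and dose of the month just ended, and would not extend the result to the higher dose. That needs no new rule in the plan. Naming the screening visit as visit 1 would spare readers the count, but it is clarifying detail only.

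This rests on one assumption, that screening is visit 1, inferred from the visit counts. If screening were visit 0, the third report's reason for the dose order would conflict with the draw schedule, and the three accounts of the draws would have to be reconciled. No estimate, test or sample size changes on either reading.
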